3.9 Immunogenicity

The IM results will be analyzed by summarizing the number and percentage of subjects who develop positive ADA. A descriptive summary of actual ADA titers by visit will also be provided.

3.10 Pharmacokinetics

The PK components of the clinical study report will be generated and reported by MedImmune's Clinical Pharmacology & DMPK group.

4 INTERIM ANALYSIS

No interim analysis will be performed for the CD1145 study.

5 VERSION HISTORY

Version	Date	Summary of Changes	Reason for Change
1.0	08Apr2013	Initial document	Initial document
2.0	26Oct2017	
Layout changedCoding dictionary for medications is changed to WHO Drug Dictionary from AZ-DD	
New SAP templateTo be consistent with phase 3 studies.

6 APPENDIX

Appendix E

REFERENCE RANGES AND TELVC FOR LABORATORY VALUES

Parameter	Unit	Low value	Low decrease	High value	High increase
Haematology					
Haemoglobin	g/L	≤6	NA	≥20	NA
		≤7 and decrease from BL ≥1.5			
Haematocrit	V/V	≤0.18	NA	≥0.64	NA
		≤0.21 and decrease from BL ≥15%			
WBC	10E9/L	≤2, <1	NA	≥20	NA
Neutrophils	10E9/L	<0.5	NA	≥20	NA
		<1.0 and decrease from BL ≥0.5			
Lymphocyte	10E9/L	≤0.5, ≤0.25	NA	≥10.0	NA
Monocytes	10E9/L	NA	NA	≥1.4, ≥5.0	NA
Eosinophils	10E9/L	NA	NA	≥1.5, ≥5.0	NA
Basophils	10E9/L	NA	NA	≥1.0, ≥2.0	NA
Platelet Count	10E9/L	≤20		≥600	NA
		≤50 and decrease from BL ≥25			
INR		NA	NA	≥4.5	NA
Biochemistry					
ALT	IU/L	NA	NA	≥3 x ULN, ≥5 x ULN	NA
AST	IU/L	NA	NA	≥3 x ULN, ≥5 x ULN	NA
ALP	IU/L	NA	NA	≥3 x ULN	NA
CK	IU/L	NA	NA	≥500, ≥2000	NA
GGT	IU/L	NA	NA	≥5 x ULN	NA
Total Bilirubin	μmol/L	NA	NA	≥2 x ULN	NA

Parameter	Unit	Low value	Low decrease	High value	High increase
Albumin	g/L	≤ 20	NA	≥ 100	NA
		≤ 25 and decrease from BL	≥ 10	≥ 70 and increase from BL	≥ 10
BUN	mmol/L	NA	NA	≥ 18	NA
Creatinine	umol/L	NA	NA	$\geq 140, \geq 190$	NA
Sodium	mmol/L	≤ 132	NA	≥ 152	NA
Potassium	mmol/L	≤ 3	NA	≥ 5.5	NA
Chloride	mmol/L	≤ 90	NA	≥ 120	NA
Fasting Glucose	mmol/L	≤ 2.5	NA	$\geq 7.0, \geq 11.1$	NA
Total Cholesterol	mmol/L	NA	NA	≥ 7.25	NA
Urinalysis					
Urine protein/ creatinine ratio	g/mmol	NA	NA	≥ 0.395	NA
Fasting lipid profile					
HDL	mmol/L	≤ 0.8	NA	NA	NA
LDL	mmol/L	NA	NA	≥ 5.2	NA
Triglycerides	mmol/L	NA	NA	$\geq 3.6, \geq 5.4$	NA

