5.2.5 Clinical Laboratory Tests

Clinical laboratory safety tests will be performed in a central clinical laboratory. Urine pregnancy tests may be performed at the site using a licensed test (dipstick). Abnormal laboratory results should be repeated as soon as possible (preferably within 24 to 48 hours).

Subjects will be required to fast for at least 8 hours prior to the assessment of lipid profile (high-density lipoprotein [HDL], low-density lipoprotein [LDL], cholesterol, and triglycerides) according to the Schedule of Study Procedures (Table 5.1-1 and Table 5.1-2).

The following clinical laboratory tests will be performed (see Table 5.1-1 and Table 5.1-2 for the schedule of tests):

Serum Chemistry

- Calcium
- Chloride
- Potassium
- Sodium
- Aspartate transaminase (AST)
- Alanine transaminase (ALT)
- Alkaline phosphatase (ALP)

- Gamma glutamyl transferase (GGT)
- Blood urea nitrogen (BUN)
- Creatinine
- Total bilirubin (reflexively fractionated if elevated)
- Glucose
- Albumin
- Creatine kinase (CK)

Note for serum chemistries: Tests for AST, ALT, ALP, and total bilirubin must be conducted concurrently and assessed concurrently.

Hematology

- White blood cell (WBC) count with differential
- Red blood cell (RBC) count
- Hematocrit
- Hemoglobin

- Platelet count
- Mean corpuscular volume (MCV)
- Mean corpuscular hemoglobin concentration (MCHC)

Urinalysis

- Color
- Glucose

Ketones

Blood

- Appearance
- Specific gravity
- pH
- Bilirubin
- Protein
- Microscopy including WBC/high power field (HPF), RBC/HPF

Pregnancy Test (females of childbearing potential only)

• Urine human chorionic gonadotropin (HCG)

Note: Any female subject who is postmenopausal based on documented results from the serum follicle-stimulating hormone test will not require urine HCG tests in this study. Any female subject who feels that they have had a change in status to postmenopausal at any point during this study can request a serum follicle-stimulating hormone test. If the results show that the subject is postmenopausal, then the subject will not require any further urine HCG tests.

Additional Tests

- Lipid profile (HDL, LDL, cholesterol, triglycerides, direct LDL when triglycerides are > 400 mg/dL) requiring a fasting blood sample of at least 8 hours
- Immunology profile: ANA, extractable nuclear antigen (RNP, Sm, SSA, SSB), quantitative immunoglobulins

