3.8.5 Clinical Laboratory Evaluation

Hematology, serum chemistry, lipid profile (HDL, LDL, cholesterol, and triglycerides), and urinalysis parameters will be collected in this study. The hematology, serum chemistry, and lipid profile parameters as well as their changes from baseline will be summarized with descriptive statistics by visit. The shift from baseline in hematology, serum chemistry, lipid profile, and urinalysis parameters will be summarized by visit.

Treatment-emergent laboratory/vital signs changes (TELVC) will be defined for post-baseline values according to the reference ranges given in **Appendix E**. Number of subjects with TELVC will be summarized by visit.

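### The haemoglobin TELVC limits in SAP Appendix E are labelled g/L but make sense only in g/dL

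*SAP*

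**What the plan says.** Appendix E of the SAP sets the laboratory limits. The haemoglobin row reads "Haemoglobin g/L ≤6 NA ≥20 NA", with a second low criterion of "≤7 and decrease from BL ≥1.5". The row below it reads "Haematocrit V/V ≤0.18 NA ≥0.64 NA", with a second low criterion of "≤0.21 and decrease from BL ≥15" per cent.

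SAP 3.8.5 applies these limits directly: TELVC "will be defined for post-baseline values according to the reference ranges given in" Appendix E. It then specifies the output: "Number of subjects with TELVC will be summarized by visit". The same section also plans descriptive summaries of the haematology values, and "The shift from baseline in hematology, serum chemistry, lipid profile, and urinalysis parameters will be summarized by visit".

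Neither document converts the haemoglobin unit or says that haemoglobin is analysed in g/dL. The SAP version history (Section 5) lists a layout change and a change of medication dictionary, but no correction to this row.

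**The concern.** Haemoglobin and haematocrit are tied together by the concentration of haemoglobin in red cells (MCHC), which is haemoglobin divided by haematocrit. Limits meant to flag the same degree of abnormality in both must agree through that ratio. In Appendix E they do not agree in the stated unit.

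Haematology is one of the supporting variables for the primary safety objective (Protocol 7.3.1). If the laboratory dataset holds haemoglobin in g/L, a programmer who follows the SAP to the letter will produce a haemoglobin TELVC line that says nothing about the subjects. A sample that the haematocrit row counts as severely low would meet the haemoglobin high limit in the same table.

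**Working it through.** **Inputs.** From SAP Appendix E: haemoglobin limits 6, 7 (with a fall of 1.5) and 20, labelled g/L; haematocrit limits 0.18, 0.21 and 0.64 V/V. Protocol 5.2.5 lists MCHC among the haematology tests but gives no range. Assumption from outside the documents: MCHC is about 300-370 g/L. A wider range of 280-380 g/L is used as a sensitivity check.

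**Step 1: MCHC implied by the paired limits (haemoglobin limit / haematocrit limit).**

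| Pair | As labelled (g/L) | If the limits are g/dL (×10, in g/L) |
|---|---|---|
| Low | 6 / 0.18 = 33.3 | 60 / 0.18 = 333 |
| Low with fall | 7 / 0.21 = 33.3 | 70 / 0.21 = 333 |
| High | 20 / 0.64 = 31.3 | 200 / 0.64 = 313 |

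The ratio is nearly constant, which suggests that the two rows were set as matched pairs. Only the g/dL reading falls in the assumed range.

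**Step 2: haemoglobin expected at the haematocrit limits (haematocrit × MCHC, 300-370 g/L).**

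- 0.18 gives 54-67 g/L, which is 9.0-11.1 times the stated 6.
- 0.21 gives 63-78 g/L, which is 9.0-11.1 times the stated 7.
- 0.64 gives 192-237 g/L, which is 9.6-11.8 times the stated 20.

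So a sample exactly at the haematocrit low limit has haemoglobin of 54-67 g/L. As labelled, it fails the haemoglobin low limit (6) and meets the high limit (20).

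**Step 3: haematocrit needed to reach the literal limits (haemoglobin / MCHC, 300-370 g/L).**

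- 6 g/L needs 0.016-0.020, which is 9-11 times below the table's own low limit of 0.18.
- 20 g/L needs 0.054-0.067, which is 30-37% of that low limit.

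With 280-380 g/L these become 0.016-0.021 and 0.053-0.071, so the conclusion is the same.

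**Step 4: how far the assumption could move.** For a sample with haematocrit above 0.18 to have haemoglobin below 20 g/L, MCHC would have to be below 20 / 0.18 = 111 g/L.

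**Step 5: the literal rule on example values.** Haemoglobin of 80, 100, 120, 140 and 160 g/L all meet the high limit and none meets a low limit. Expressed as 8-16 g/dL, the same values trigger no flag.

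**Step 6: where it would show.** Haematology is scheduled after baseline at Weeks 4 and 8 (2 visits), every 12 weeks from Week 12 to Week 144 (12), Week 156 (1), and Visits 41 and 43 (2): 2 + 12 + 1 + 2 = 17 visits. With about 240 subjects and no dropout that is about 240 × 17 = 4,080 subject-visits. This is a scale for the table, not a forecast.

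**The case against.** The strongest reply is that nothing shows the error reaching the results. The documents do not give the unit of the haemoglobin data. If it is g/dL, the numbers work as intended and only a label is wrong. The statistical programming plan, which holds the table specifications, is not available to us and may already be right. There is also a hint of conventional units: Protocol 5.2.5 gives a triglyceride threshold in mg/dL. With g/L data the fault would be conspicuous, as nearly every subject would be high or the row would be empty.

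The reach is also small. Safety is judged mainly on adverse events, with no formal testing. Haemoglobin values, changes and shifts are reported anyway. The haematocrit row flags equivalent severe anaemia. Investigators report laboratory abnormalities as adverse events on their own judgement, and no dosing or monitoring decision is tied to TELVC. Finally, a letter lost when the PDF was read cannot be fully excluded.

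Much of this stands as a limit on the consequence. It does not rescue the row. Appendix E states triglycerides in mmol/L and most other units in SI form, so g/L haemoglobin data are entirely plausible. The SAP is the governing specification and should not depend on a programmer noticing. The other units in the table read cleanly, including albumin in g/L, so a reading error is unlikely. The subject-visit figure should be read loosely: 240 is approximate (307 × 0.8 = 245.6), and the number flagged high depends on how values already beyond the limit at baseline are treated.

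**Conclusion.** The row is wrong as written. Its limits are about ten times too small for the stated unit: 9-11 times for the low limits and 9.6-11.8 times for the high limit. They agree with the haematocrit row only as g/dL.

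Applied literally to g/L data, the low criteria would flag practically nobody. The high criterion would flag essentially everyone, or almost nobody if values already beyond it at baseline are not counted as treatment-emergent. In neither case does the row discriminate.

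The conclusion rests on one outside assumption, an MCHC of 300-370 g/L. It is not sensitive to that choice: the result is unchanged over 280-380 g/L, and MCHC would have to be below 111 g/L to overturn it. The effect on results is conditional on the dataset being in g/L and is confined to the haemoglobin TELVC counts. It should be fixed because SAP 3.8.5 applies these limits directly to a reported safety table. It does not threaten the main safety conclusions.

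**What to change.** Make the unit and the limits agree, in one of two equivalent ways:

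- relabel the row g/dL and keep 6, 7 (fall of 1.5) and 20; or
- keep g/L and multiply all four numbers by ten, giving ≤60, ≤70 with a fall from baseline of at least 15, and ≥200.

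Check the haemoglobin unit in the laboratory dataset first, choose the version that matches it, and carry the same unit into the statistical programming plan. These are analysis flags, so the change sets no clinical rule. It costs one table row and one check of the dataset, and needs no new data.

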Appendix F

REFERENCE RANGES AND TELVC FOR VITAL SIGNS

Parameter	Unit	Low value	Low decrease	High value	High increase
Pulse	Beats per minute	≤ 50 ≤ 50 and decrease from BL ≥ 20	NA	≥ 120 ≥ 120 and increase from BL ≥ 20	NA
Systolic blood pressure	mmHg	≤ 90 ≤ 90 and decrease from BL ≥ 20	NA	≥ 160 ≥ 160 and increase from BL ≥ 20	NA
Diastolic blood pressure	mmHg	≤ 50 ≤ 50 and decrease from BL ≥ 10	NA	≥ 100 ≥ 100 and increase from BL ≥ 10	NA
